### 6.1.3 Duration of treatment

**Note for CSP v2.0: See Section 10.3.1 for the duration of open-label durvalumab treatment.**

All treatment will be administered beginning on Day 1 for up to 26 cycles (up to a total of 24 months) of durvalumab or placebo q4w, unless there is unacceptable toxicity, withdrawal of consent, or another discontinuation criterion is met.

Treatment will be stopped when a patient has received a total of 24 months of therapy (26 cycles of treatment) or upon evidence of RECIST 1.1-defined disease recurrence using Investigator’s assessments, whichever occurs first.

During the treatment period, patients who are clinically stable at an initial RECIST 1.1-defined disease recurrence may continue to receive study treatment at the discretion of the Investigator until the follow-up scan.

Patients with rapid tumor progression or with symptomatic progression that requires urgent medical intervention (eg, central nervous system metastasis, respiratory failure due

to tumor compression, or spinal cord compression) will not be eligible for continuing durvalumab or placebo.

Patients who AstraZeneca and/or the Investigator determine may not continue treatment after RECIST 1.1-defined disease recurrence will be followed up for survival until the completion of the study. Patients who have discontinued treatment due to toxicity or symptomatic deterioration, or who have commenced subsequent anticancer therapy, will be followed up with tumor assessments until RECIST 1.1-defined disease recurrence plus an additional follow-up scan or until death (whichever comes first) and followed for survival.

Patients may not receive retreatment in this study.

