## 9.2 Sample size determination

Approximately 284 patients with stage II-III NSCLC who are MRD+ will be randomized 1:1 to durvalumab or placebo. Of the patients randomized into the study, at least 170 patients are required to be PD-L1 TC $\geq$ 1% at study entry. The primary analysis is planned to be performed in the PD-L1 TC $\geq$ 1% analysis set. An analysis on the FAS (all MRD+ stage II-III NSCLC patients randomized) will be performed as a secondary objective of the study. Randomization will be stratified by PD-L1 status (TC<1% vs TC $\geq$ 1%), time from the start of surveillance to the emergence of MRD ( $\leq$ 6 months vs >6 months), and prior neoadjuvant immunotherapy (Yes vs No). In this study, the start of surveillance is defined as the day the plasma sample used to determine a patient's MRD status post-curative intent therapy is collected.

The study is sized for the primary endpoint of DFS in the PD-L1 TC $\geq$ 1% analysis set and for the secondary endpoint of DFS in the FAS.

The analysis of the primary endpoint (DFS) will occur when approximately 118 DFS events have occurred (69% maturity) in the PD-L1 TC $\geq$ 1% analysis set. If the true DFS HR is 0.55 in the PD-L1 TC $\geq$ 1% analysis set, the study will provide at least 90% power to demonstrate a statistically significant difference for DFS with overall 2-sided significance level of 5%; this translates to 3.2-month benefit in median DFS over 4 months on placebo, or 8.4% difference in 2-year DFS rate over 1.5% on placebo, if DFS is exponentially distributed. The smallest treatment difference that would be statistically significant is an HR of 0.7.

The study is also sized to provide at least 90% power for the DFS endpoint in the FAS. The analysis will be performed at the same time as the primary analysis, when it is expected that approximately 197 DFS events have occurred (69% maturity) in the FAS. If the true DFS HR is 0.63 in this population, this will provide at least 90% power to demonstrate a statistically significant difference for DFS, assuming overall 5% 2-sided

significance level; this translates to a 2.3-month benefit in median DFS over 4 months on placebo, or 5.6% difference in 2-year DFS rate over 1.5% on placebo, if DFS is exponentially distributed. The smallest treatment difference that would be statistically significant is an HR of 0.76.

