### **9.5.2 Safety analyses**

All safety and tolerability data will be presented by treatment arm using the SAS.

Data from all cycles of treatment will be combined in the presentation of safety data. AEs (both in terms of Medical Dictionary for Regulatory Activities [MedDRA] preferred terms and CTCAE grade) will be listed individually by patient. The number of patients experiencing each AE will be summarized by treatment arm and CTCAE grade. Additionally, data presentations of the rate of AEs per person-years at risk may be produced.

Other safety data will be assessed in terms of physical examination, clinical chemistry, hematology, vital signs, and ECGs (conducted at baseline and as clinically indicated). Exposure to durvalumab and placebo will be summarized. Time on study and durvalumab, including any dose delays, will also be summarized. At the end of the study, appropriate summaries of all safety data will be produced, as defined in the SAP.

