	
Section 4.2.4 – revised Progression-free survival description to be listed only.
 
Section 4.2.5 – revised time to first and second subsequent therapy or death description to be listed only.
 
Section 4.2.6 – Data Cut-Offs revised as per CSP V2.0.
 
CCI [REDACTED]
 
• CCI [REDACTED]• CCI [REDACTED] 
CCI [REDACTED]
 
Section 4.2.9
 
• removed section on summary of long term tolerability.• revised wording for AE with outcome of death, as per AZSOL. 
Section 4.2.9.1
 
• removed summaries for time to onset and duration of the first AE, event rate, and longer-term toxicity profile.• replaced summary table on “most common AEs with CTCAE grade 3 or 4” with summary table on “most common AEs with maximum CTCAE grade 3 or 4”.• summary for death limited to all deaths on the FAS. 
Section 4.2.9.2 – removed AESI/AEPI summaries leading to steroid use, discontinuation of study treatment and dose delay of study treatment.
 
Section 4.2.9.3
 
• removed all graphical presentations of laboratory data, as well as summaries of absolute value and change from baseline in hematology and chemistry, and urinalysis shift table.• Thyroid function tests: removed summaries on elevated on-treatment TSH. Added shift tables to maximum and minimum on-treatment.• Renal function tests: removed summaries of CrCl reversibility. 
Section 4.2.9.4 – revised electrocardiograms description to be listed only.
 
Section 4.2.9.5 – revised vital signs description to be listed only.
 
Section 4.2.11 – added a summary of subsequent anti-cancer therapy.
 
Section 4.2.13 – removed sensitivity analyses.
 
Section 4.4 – Observation period removed as per CSP V2.0.
 
Section 5.1 – aligned with CSP V2.0, no interim analyses are planned.
 
Section 5.2 – added provision of a final safety report post-DBL.
 
Section 6 – updated to include reference to the CSP amendment.

Date	Brief description of change
	
Section 7 – removed references no longer used in this document due to updates as listed above.
 
Appendix B – revised imputation for completely missing medication/therapy end dates, partial death dates.
 
Minor formatting changes throughout.
 
AZ Global Product Statistician signatory updated.

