1.1.2 Secondary Objectives

Secondary/Safety objective:	Endpoint/variables:
To assess the safety and tolerability profile of durvalumab monotherapy compared to placebo	AEs, physical examinations, vital signs, and laboratory findings

AE Adverse event.

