1.2 Study Design

This is a Phase III, randomized, multicenter, double-blind, placebo-controlled study to evaluate the efficacy and safety of durvalumab adjuvant therapy compared to placebo in patients with stage II-III non-small cell lung cancer (NSCLC) who have undergone curative intent therapy (complete resection ± neoadjuvant and/or adjuvant therapy), who have no evidence of RECIST 1.1- defined disease recurrence, and who become minimal residual disease-positive (MRD+) during a 96-week surveillance period.

Prior to CSP V2.0, the study was designed to screen approximately CCI patients and randomize approximately CCI MRD+ patients with stage II-III NSCLC whose tumors are epidermal growth factor receptor (EGFR) and anaplastic lymphoma kinase (ALK) wild type,

and who have completed curative intent therapy. Randomized patients were to include approximately **CC1** PD-L1 TC \geq 1% and **CC1** PD-L1 TC<1% patients.

Following the decision to close recruitment early, a total of 416 patients have signed informed consent for the study and approximately 30 are expected to be randomized within the study.

Eligible patients will be enrolled in a 96-week surveillance period during which they will be monitored for the emergence of MRD. During surveillance, the patient will be evaluated for MRD by plasma sampling every 6 weeks (q6w \pm 3d) and will receive computed tomography (CT) scans every 12 weeks (q12w \pm 1w) for up to 96 weeks.

Patients who become MRD+ during surveillance (including cases where analysis of the first plasma sample collected [marking the start of surveillance] returns an MRD+ status) will undergo a second screening period. Note: Patients who received prior neoadjuvant immunotherapy must be MRD- based on analysis of the first plasma sample collected (which marks the start of surveillance).

MRD+ patients will be randomized 1:1 to treatment with durvalumab monotherapy 1500 mg or placebo every 4 weeks (q4w) intravenously (IV). Randomization will be stratified by PD-L1 status (TC<1% vs TC \geq 1%), time from start of surveillance to emergence of MRD (\leq 6 months vs >6 months), and prior neoadjuvant immunotherapy (Yes vs No).

[figure not shown]
Patients will be treated for up to a total of 24 months (26 cycles), until disease recurrence, or until other specific treatment discontinuation criteria are met (whichever comes first).

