4.2.9.1 Adverse Events (AEs)

All AEs, both in terms of current MedDRA PT and CTCAE grade, will be summarized descriptively by count (n) and percentage (%) for each treatment group. Any AE occurring before study treatment (i.e. before the administration of the first dose of durvalumab/placebo) will be included in the AE listings, but will not be included in the summary tables (unless otherwise stated). These will be referred to as ‘pre-treatment’. However, any AE occurring before the administration of the first dose of study treatment on study day 1 that increases in severity after the first dose will be regarded as treatment-emergent and thus will be included in the majority of summary tables.

Adverse events observed up until 90 days following discontinuation of study treatment (i.e. the last dose of durvalumab/placebo) or until the initiation of the first subsequent anti-cancer therapy (including radiotherapy, except for palliative radiotherapy) following discontinuation of study treatment (whichever occurs first) will be used for the reporting of the AE summary tables. This will more accurately depict AEs attributable to study treatment only, as a number of AEs up to 90 days following discontinuation of study treatment are likely to be attributable to subsequent therapy.

Any AEs that occur between the start of subsequent anti-cancer therapy and up until 90 days following discontinuation of study treatment will be flagged in the data listings.

All reported AEs will be listed along with the date of onset, date of resolution (if AE is resolved) and Investigator’s assessment of severity and relationship to durvalumab/placebo. Frequencies and percentages of patients reporting each PT will be presented (i.e. multiple events per patient will not be accounted for apart from on the episode level summaries).

Summary information (the number and percentage of patients by system organ class (SOC) and PT separated by treatment group) will be tabulated for:

- All AEs

- All AEs possibly related to study treatment (as determined by the reporting Investigator)
- AEs with maximum CTCAE grade 3 or 4
- AEs with maximum CTCAE grade 3 or 4, possibly related to study treatment (as determined by the reporting Investigator)
- SAEs with outcome of death
- SAEs with outcome of death possibly related to study treatment (as determined by the reporting Investigator)
- All SAEs
- All SAEs possibly related to study treatment (as determined by the reporting Investigator)

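### SAP v2.0 gives no AE table a person-time denominator, so if durvalumab delays recurrence the crude percentages may modestly overstate its relative AE burden

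*SAP*

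**What the plan says.** SAP Section 1.1.2 words the one secondary objective as "To assess the safety and tolerability profile of durvalumab monotherapy compared to placebo". The SAP calls all analyses descriptive and exploratory and expects about 30 patients to be randomized (Sections 1 and 1.2).

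Protocol Section 6.1.3 stops treatment after 26 cycles or "upon evidence of RECIST 1.1-defined disease recurrence", whichever is first, subject to other discontinuation criteria. SAP Sections 3.3 and 4.2.9.1 count AEs to 90 days after the last dose, or to the first subsequent anti-cancer therapy if that is sooner.

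For the AE tables, SAP Section 4.2.9.1 states: "Frequencies and percentages of patients reporting each PT will be presented". It adds an overall count of episodes per category. Section 4.2.9.2 summarizes AEs of special or possible interest (AESI/AEPI) and immune-mediated AEs (imAEs) as numbers and percentages of patients, with time to onset and resolution for imAEs. Section 4.2.12 summarizes exposure by arm and plots the percentage still on treatment over time.

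Protocol Section 9.5.2 allows more: "Additionally, data presentations of the rate of AEs per person-years at risk may be produced". The SAP amendment history for V2.0 records the reverse step: "removed summaries for time to onset and duration of the first AE, event rate, and longer-term toxicity profile".

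**The concern.** A patient who recurs stops treatment, and the AE window closes at most 90 days later, or sooner if new therapy starts. The number of months in which an AE can be counted therefore depends on recurrence. The original sizing expected recurrence to differ by arm: for the full analysis set, Protocol Section 9.2 says "this translates to a 2.3-month benefit in median DFS over 4 months on placebo".

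Under that expectation, an event with the same monthly hazard in both arms has longer to appear on durvalumab. Background complaints such as cough or fatigue would then show a higher crude percentage there with no drug effect. Episode counts without person-time share the problem. Safety against placebo is the only secondary objective left, and a descriptive report is read straight from its tables, so a denominator matters even without formal testing.

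**Working it through.** **1. Reproduce the design figures.** Schoenfeld events at two-sided 5%, 90% power and 1:1 allocation: d = 4(1.960 + 1.282)² / (ln HR)².
- HR 0.63: 42.03 / 0.2135 = 197 (Protocol 9.2: 197).
- HR 0.55: 42.03 / 0.3574 = 118 (Protocol 9.2: 118).
- Exponential medians: 4/0.63 = 6.35 months, a gain of 2.3 as stated; 4/0.55 = 7.27, a gain of 3.3 against 3.2 stated (rounding).

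**2. Inputs for the AE check.** The placebo recurrence hazard is h = ln 2/4 = 0.173 per month, and on durvalumab 0.63h = 0.109 or 0.55h = 0.095. The tail is 90 days = 2.96 months. The documents give no AE rate, so these are assumptions: a constant first-event hazard r, equal in both arms, of 0.02 to 0.5 per month; stopping driven by recurrence only; no cut at subsequent therapy; 15 patients per arm.

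**3. Full 24-month cap.** With recurrence hazard λ and T = min(recurrence, 24), mean time on treatment is (1 − e^(−24λ))/λ. This is 5.7 months on placebo and 8.5 on durvalumab at HR 0.63, a ratio of 1.50. Adding the tail gives 8.6 and 11.4 months, a ratio of 1.33.

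Crude percentage = 1 − e^(−2.96r) × [λ/(λ+r) × (1 − e^(−24(λ+r))) + e^(−24(λ+r))].

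For r = 0.05:
- Placebo: 1 − 0.862 × 0.777 = 33.0%.
- Durvalumab, HR 0.63: 1 − 0.862 × 0.693 = 40.3%.

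| r per month | Placebo % | Durvalumab %, HR 0.63 | Excess, points |
|---|---|---|---|
| 0.02 | 15.4 | 19.7 | 4.3 |
| 0.05 | 33.0 | 40.3 | 7.3 |
| 0.10 | 52.8 | 60.9 | 8.1 |
| 0.20 | 74.3 | 80.4 | 6.1 |
| 0.50 | 94.1 | 95.9 | 1.8 |

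At HR 0.55 the largest excess is 10.6 points.

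**4. Early closure.** Suppose follow-up to the data cut-off, C, is uniform on 1 to 16 months (assumed), and the AE window is min(recurrence + 2.96, C). For r = 0.05 the crude percentage is 24.5% on placebo against 26.8% (HR 0.63) or 27.4% (HR 0.55), an excess of 2.3 or 2.9 points. In 15 patients that is 15 × 0.023 = 0.3 or 15 × 0.029 = 0.4 of a patient. With a fixed 12-month cap instead, the excess at HR 0.63 is about 2 to 6.5 points over r = 0.02 to 0.5.

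**5. What a rate shows.** Patients with an event divided by time to first event or end of window has expectation r in both arms under these assumptions: 0.05 × 12 = 0.60 per patient-year, whatever the HR.

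**6. Where the excess shrinks.**
- HR 1: zero.
- Hazard of 0.2 per month confined to the first 3 months: 45.1% in both arms. Confined to 6 months: 64.8% against 66.5%.
- If 10% of durvalumab patients stop for AEs (the proportion in Protocol 2.3.2.1), the time-on-treatment ratio falls from 1.50 to 1.37.

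**7. Noise.** For step 4 at HR 0.63, the 95% half-width of the difference is 1.96 × √(0.245 × 0.755/15 + 0.268 × 0.732/15) = 31 points. In step 3 it ranges from about 15 to 35. With a 24-month cap, HR 0.63 and r from 0.05 to 0.20, durvalumab has the higher crude percentage in 57–61% of trials this size, the lower in 26–27%, and a tie otherwise.

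**The case against.** The strongest reply is that the plan already lets a reader judge exposure. It gives total, actual and cumulative exposure by arm, a time-on-treatment plot, episode counts, imAE time to onset and dated AE listings. With about 30 patients, any imbalance can be seen. This stands against any claim that only crude percentages are reported. It does not supply the missing denominator: none of these outputs relates an AE count to time at risk, and exposure time differs from AE time at risk because of the 90-day tail and the cut at subsequent therapy.

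Second, SAP Section 1 restates the objective as reporting safety in both arms, nothing is formally tested, and dropping an optional output after early closure is a recorded choice. That also stands. Because Protocol 9.5.2 says only that rates may be produced, a reader who inferred a conflict between SAP and protocol would be wrong.

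Third, rates have a fault of their own. If immune-mediated events cluster early, longer durvalumab person-time dilutes the rate and could hide harm. This is correct and shapes the fix.

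A reader might also infer that the tables will show an excess on durvalumab from longer observation alone. The documents do not support that: it requires a true DFS benefit, a steady event rate and no offsetting stops for toxicity. Counting AEs only to recurrence gives a larger contrast, 0.05/(0.05 + 0.173) = 22% against 0.05/(0.05 + 0.109) = 31%, but it ignores the SAP's 90-day window and the early closure.

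**Conclusion.** The point holds as a conditional weakness in an analysis choice. AE time at risk depends on recurrence, and no planned AE table has a person-time denominator. If the design hazard ratios are true, crude n (%) may overstate durvalumab's relative burden for steady background events. The expected size is 2 to 3 points for a 5%-per-month event under the assumed early closure, and 2 to 8 points at HR 0.63 had follow-up run to 24 months. With about 15 patients per arm, sampling noise exceeds this, so no safety conclusion should turn on it alone. The figures rest on exponential recurrence, a constant and equal AE hazard, the assumed follow-up, no cut at subsequent therapy, and no treatment continued past recurrence, although Protocol 6.1.3 allows clinically stable patients to continue until the follow-up scan.

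**What to change.** In SAP Section 4.2.9.1, add by arm, beside n (%) and not in place of it:
- patients with an event;
- patient-years at risk, from first dose to first event or the end of the on-treatment window;
- the exposure-adjusted incidence rate.

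Do this for any AE, AEs of maximum grade 3 or 4, SAEs, and AEs leading to discontinuation. In Section 4.2.9.2, show rates for AESI/AEPI and imAEs only beside n (%) and, for imAEs, beside the planned time to onset, since longer person-time can dilute early events.

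The cost is a few lines of SAP text and one or two tables from dates the planned outputs already need. The drawbacks are a roughly constant hazard assumption and low precision; a table note should state both.

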4.2.9.2 AEs of Special Interest and Possible Interest

Preferred terms used to identify AESI/AEPI will be listed before DBL and documented in the Trial Master File. Grouped summary tables of certain MedDRA PTs will be produced and may also show the individual PTs which constitute each AESI grouping. Groupings will be based on PTs provided by the medical team prior to DBL, and a listing of the PTs in each grouping will be provided.

Summaries of the above-mentioned grouped AE categories will include number (%) of patients who have:

- Any AESI/AEPI

- Any AESI/AEPI by SOC, PT and maximum CTCAE grade
- Any AESI/AEPI of maximum CTCAE grade 3 or 4
- Any serious AESI/AEPI
- Any serious AESI/AEPI with outcome of death
- Any AESI/AEPI possibly related to study treatment
- Any AESI/AEPI leading to concomitant medication use (high dose steroids)
- Any AESI/AEPI leading to concomitant medication use (endocrine therapy)
- Any AESI/AEPI leading to concomitant medication use (other immunosuppressants)

An overall AESI/AEPI summary will be presented, including number and percentage of patients in each of these categories. Any AESI/AEPI presented by outcome will also be provided.

In addition, a listing of key patient information for AESI/AEPI will be provided.

Immune-mediated Adverse events (imAEs)

The imAEs (as classified by the Sponsor) will be summarized in the similar manner as for the summaries for AESI/AEPI described above. Time to onset and resolution of imAE will also be summarized. Further details are covered in the latest version of the imAE charter.

4.2.9.3 Laboratory Assessments

Data obtained up until the 90 days following discontinuation of study treatment (i.e. durvalumab/placebo) or until the initiation of subsequent anti-cancer therapy (including radiotherapy, except for palliative radiotherapy) following discontinuation of study treatment (whichever occurs first) will be used for reporting. This will more accurately depict laboratory toxicities attributable to study treatment only as some toxicities up to 90 days following discontinuation of the study treatment are likely to be attributable to subsequent therapy. Any data post 90 days after the last dose of the study treatment will not be summarized.

Data summaries will be provided in SI units.

Shift tables for laboratory values by worst CTCAE grade will be produced, and for specific parameters separate shift tables indicating hyper- and hypo- directionality of change will be produced. The laboratory parameters for which CTCAE grade shift outputs will be produced are:

- Hematology: Hemoglobin (low and high); Leukocytes (low and high); Lymphocytes (low and high - count, absolute); Neutrophils (low - count, absolute); Platelets (low)

- Clinical chemistry: Alanine aminotransferase (ALT) (high), Aspartate aminotransferase (AST) (high), Alkaline phosphatase (ALP) (high), Total Bilirubin (high), Albumin (low), Magnesium (hypo and hyper), Sodium (hypo and hyper), Potassium (hypo and hyper), Corrected Calcium (hypo and hyper), Glucose (low), Creatinine (high), GGT (high), Amylase (high), Lipase (high)

In addition, all laboratory data will be listed.

Liver Enzyme Elevations and Hy's Law

The following summaries will include the number (%) of patients who have:

- Elevated ALT, AST, and Total bilirubin on-treatment
 - ALT $\geq 3\times - \leq 5\times$, $> 5\times - \leq 8\times$, $> 8\times - \leq 10\times$, $> 10\times - \leq 20\times$, and $> 20\times$ ULN on-treatment
 - AST $\geq 3\times - \leq 5\times$, $> 5\times - \leq 8\times$, $> 8\times - \leq 10\times$, $> 10\times - \leq 20\times$, and $> 20\times$ ULN on-treatment
 - Total bilirubin $\geq 2\times - \leq 3\times$, $> 3\times - \leq 5\times$, $> 5\times$ ULN on-treatment
 - ALT or AST $\geq 3\times - \leq 5\times$, $> 5\times - \leq 8\times$, $> 8\times - \leq 10\times$, $> 10\times - \leq 20\times$, $> 20\times$ ULN on-treatment
 - ALT or AST $\geq 3\times$ ULN and Total bilirubin $\geq 2\times$ ULN on-treatment (Potential Hy's law): The onset date of ALT or AST elevation should be prior to or on the date of Total Bilirubin elevation

Individual patient data where ALT or AST (i.e. $\geq 3\times$ ULN) plus Total Bilirubin (i.e. $\geq 2\times$ ULN) are elevated at any time will be listed also.

Assessment of Thyroid Function Test Results

The following summaries will include the number and percentage of patients who have elevated or low thyroid stimulating hormone (TSH).

- TSH $> \text{ULN}$
- TSH $> \text{ULN}$ with TSH $\leq \text{ULN}$ at baseline
- TSH $> 3 \times \text{ULN}$
- TSH $> 3 \times \text{ULN}$ with TSH $\leq \text{ULN}$ at baseline
- TSH $> 10 \times \text{ULN}$
- TSH $> 10 \times \text{ULN}$ with TSH $\leq \text{ULN}$ at baseline

- TSH < LLN
- TSH < LLN with TSH \geq LLN at baseline

In addition, summaries will include shift tables comparing baseline value to maximum on-treatment value and baseline value to minimum on-treatment value. Thyroid function test data will be listed also.

Assessment of Renal Function Test Abnormalities

In addition to the analysis for serum creatinine, the number and percentage of patients with creatinine clearance (CrCl) rate on-treatment (derived per Section 3.3.5) meeting the following categories will be presented:

- Normal: CrCl \geq 90 mL/min
- Mild Impairment: CrCl \geq 60 - < 90 mL/min
- Moderate Impairment: CrCl \geq 30 - < 60 mL/min
- Severe Impairment: CrCl \geq 15 - < 30 mL/min
- Kidney Failure: CrCl < 15 mL/min

